8.1 Efficacy assessments

8.1.1 PASI

The PASI is the most commonly used and validated assessment for grading the severity of PSO in clinical studies (Feldman, 2004). The PASI quantifies the severity and extent of the disease and weighs these with the percentage of BSA involvement. The PASI will be completed by the Investigator electronically at the visits specified in the SoA ([Table 1-1](#)).

The percent area of involvement (BSA%) is estimated across 4 body areas; head, upper extremities, trunk, and lower extremities. Assessors will enter the degree of involvement for a given region on a scale of 0 to 6 (0=none; 1=1% to <10% affected; 2=10% to <30% affected; 3=30% to <50% affected; 4=50% to <70% affected; 5=70% to <90% affected; 6=90% to 100% affected) (Table 8-1).

The Investigator assesses the average redness, thickness, and scaliness of lesions in each body area (each on a 5-point scale); 0=none, 1=slight, 2=moderate, 3=marked, and 4=very marked.

The PASI score ranges from 0 to 72, with a higher score indicating increased disease severity.

Table 8-1: Body areas for calculation of percent BSA for PASI

Body area	Details of area	BSA	Degree of involvement of body area ^a
Head	Face, back of head	10%	0 to 6
Upper extremities	Left, right, upper lower, flexor surface, extensor surface	20%	0 to 6
Trunk	Front, back, groin	30%	0 to 6
Lower extremities	Left, right, upper lower, flexor surface, extensor surface, including buttocks	40%	0 to 6
Total		100%	

BSA=body surface area; PASI=Psoriasis Area and Severity Index

^a Where 0=none; 1=1% to <10% affected; 2=10% to <30% affected; 3=30% to <50% affected; 4=50% to <70% affected; 5=70% to <90% affected; 6=90% to 100% affected

The PASI50, PASI75, PASI90, and PASI100 responses are based on at least 50%, 75%, 90%, and 100% improvement in the PASI score, respectively. The total BSA affected by PSO will be entered as a percentage from 0 to 100.

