8.1.2 IGA

A static IGA for PSO will be used to assess disease severity in all study participants during the study. The IGA will be completed at the visits specified in the SoA (Table 1-1).

The Investigator will assess the overall severity of PSO using the following 5-point scale presented in Table 8-2 below.

Table 8-2: Five-point IGA

Score	Short descriptor	Detailed descriptor
0	Clear	No signs of PSO; postinflammatory hyperpigmentation may be present
1	Almost clear	No thickening; normal to pink coloration; no to minimal focal scaling
2	Mild	Just detectable to mild thickening; pink to light red coloration; predominately fine scaling
3	Moderate	Clearly distinguishable to moderate thickening; dull to bright red, moderate scaling
4	Severe	Severe thickening with hard edges; bright to deep dark red coloration; severe/coarse scaling covering almost all or all lesions

IGA=Investigator’s Global Assessment; PSO=psoriasis

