5.3.1 Definition of endpoints

5.3.1.1 PASI90 at Week 16

PASI90 is defined to be equal to 1 if the percentage improvement from Baseline in the PASI scores is 90% or greater and 0 if the percentage improvement from Baseline is less than 90%. This definition is introduced for the purpose of identifying study participants who respond to the treatment

(1 = responder, 0 = non-responder).

 $Percent\ Improvement\ from\ Baseline\ =\ 100\times \frac{Baseline\ PASI\ -\ Post\ Baseline\ Timepoint\ PASI}{Baseline\ PASI\ }$

The PASI is the most commonly used and validated assessment for grading the severity of PSO in clinical studies (Feldman, 2004). The PASI quantifies the severity and extent of the disease and weighs these with the percentage of BSA involvement. The PASI will be completed by the Investigator electronically at the visits specified in the protocol schedule of assessment.

The percent area of involvement (BSA%) is estimated across 4 body areas: head, upper extremities, trunk, and lower extremities. Assessors will enter the degree of involvement for a given region on a scale of 0 to 6 (0=none; 1=1% to <10% affected; 2=10% to <30% affected; 3=30% to <50% affected; 4=50% to <70% affected; 5=70% to <90% affected; 6=90% to 100% affected). This degree score is used in the calculation of PASI score as shown in Table 2. The total percent body surface area (BSA) of PSO involvement will also be estimated as a number between 0 and 100.

The Investigator assesses the average redness, thickness, and scaliness of lesions in each body area (each on a 5-point scale); 0=none, 1=slight, 2=moderate, 3=marked, and 4=very marked. The PASI score ranges from 0 to 72, with a higher score indicating increased disease severity. Detailed information of PASI scores could be found in 6.1.5.1.

			Degree of involvement of body
Body area	Details of area	BSA	area ^a
Head	Face, back of head	10%	0 to 6
Upper extremities	Left, right, upper, lower, flexor surface, extensor surface	20%	0 to 6
Trunk	Front, back, groin	30%	0 to 6
Lower extremities	Left, right, upper, lower, flexor surface, extensor surface, including buttocks	40%	0 to 6
Total		100%	

Table 2: Body areas for calculation of percent BSA for PASI

BSA=body surface area; PASI=Psoriasis Area and Severity Index

^a Where 0=none; 1=1% to <10% affected; 2=10% to <30% affected; 3=30% to <50% affected; 4=50% to <70% affected; 5=70% to <90% affected; 6=90% to 100% affected

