- If Q7 is missing and Q7a is missing, Q7 is considered unanswered (see below for details on • how this impacts the overall DLQI score).

If 1 question is left unanswered, this is scored 0 and the scores are summed and expressed as usual out of a maximum of 30. If 2 or more questions are left unanswered, the questionnaire is not scored.

A DLQI total score of 0 or 1 indicates no impact of the disease on patient's life.

The binary response variable DLQI 0/1 response (defined as a DLQI total score of 0 or 1) at Week 16 will be evaluated as a secondary endpoint.

5.4.1.1.7 Percentage of Body Surface Area (BSA) affected by PSO at Week 16

The percentage BSA affected by PSO is recorded as a number between 0 and 100 recorded at visits where skin is assessed.

The percent change from baseline in BSA is defined as:

Post Baseline BSA – Baseline BSA Percent change from Baseline = $100 \times -$ **Baseline BSA**

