# 6.1.5 Data derivation rules

# 6.1.5.1 PASI

The PASI scoring of psoriatic plaques is based on three criteria: redness (R), thickness (T), and scaliness (S). Severity is rated for each index (R, S, T) on a 0 to 4 scale (0 for no involvement up to 4 for very marked involvement). The body is divided into 4 areas comprising the head (h), upper extremities (u), trunk (t), and lower extremities (l). In each of these areas, the fraction of total surface area affected is graded on a 0-6 scale (0 for no involvement; up to 6 for 90% - 100% involvement).

The various body regions are weighted to reflect their respective proportion of BSA. The composite PASI score is then calculated by multiplying the sum of the individual-severity scores for each area by the weighted area-of-involvement score for that respective area, and then summing the four resulting quantities as follows (note for R, T, and S scores are as follows: 0 =one, 1 =slight, 2 = moderate, 3 = marked, and 4 = very marked):

$$PASI = (0.1 \times (R_h + T_h + S_h) \times A_h) + (0.2 \times (R_u + T_u + S_u) \times A_u) + (0.3 \times (R_t + T_t + S_t) \times A_t) + (0.4 \times (R_l + T_l + S_l) \times A_l)$$

where

 $R_h$ ,  $R_u$ ,  $R_t$ ,  $R_l$  = redness score of plaques on the head, upper extremities, trunk, and lower extremities, scored 0-4 respectively;

 $T_h$ ,  $T_u$ ,  $T_t$ ,  $T_l$  = thickness score of plaques on the head, upper extremities, trunk, and lower extremities, scored 0-4 respectively;

 $S_h$ ,  $S_u$ ,  $S_t$ ,  $S_l$  = scaliness score of plaques on the head, upper extremities, trunk, and lower extremities, scored 0-4 respectively;

A_h, A_u, A_t, A_l = numerical value translation of % area of psoriatic involvement score for the head, upper extremities, trunk, and lower extremities, respectively (where 0 = 0% [clear], 1 = >0% to <10%, 2 = 10% to <30%, 3 = 30% to <50%, 4 = 50% to <70%, 5 = 70% to <90%, and 6 = 90% to 100%).

The highest potential PASI score is 72 for severe disease; the lowest is 0 for no psoriasis lesions. PASI scores are treated as continuous. The percent improvement in PASI scores from Baseline will be computed as:

 $Percent\ Improvement\ from\ Baseline\ =\ 100\times \frac{Baseline\ PASI\ -\ Post\ Baseline\ Timepoint\ PASI\ Baseline\ PASI\ }{Baseline\ PASI\ }$ 

Bimekizumab

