If a study participant has experienced an improvement, this measure will be positive. If a study participant has experienced a worsening in their condition, this measure will be negative.

If a study participant is missing 1 or 2 severity measurements for a certain region, the average of the remaining severity measurement(s) within that region will be utilized to substitute for the missing severity measurement(s) in that region. If the area of affected skin and/or all severity measurements for up to 2 regions are missing, then the missing (R+T+S) x A for a region will be substituted by the average of the available (R+T+S) x A. Otherwise, the PASI will be set to missing.

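### Does the 1% floor in the PASI area grade leave trace disease ungraded and put PASI100 at risk?

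*Protocol*

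**What the plan says.** Five places define the area grade. Four agree with each other: the text of Protocol 8.1.1, the footnote to Protocol Table 8-1, the text of SAP 5.3.1.1 and the footnote to SAP Table 2 all read "0=none; 1=1% to <10% affected; 2=10% to <30% affected". The fifth, the derivation rule in SAP 6.1.5.1, reads "0 = 0% [clear], 1 = >0% to <10" per cent. All higher bands are the same everywhere.

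Two further statements matter. On data entry, Protocol 8.1.1 says "Assessors will enter the degree of involvement for a given region on a scale of 0 to 6", so the grade itself is recorded and is not computed from a percentage. On precedence, SAP 5.3.1.1 closes its description with "Detailed information of PASI scores could be found in 6.1.5.1", which leads to the version without a gap.

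**The concern.** Taken literally, the four matching statements give no grade to a region with, say, a 0.5% plaque: it is not free of disease, and it does not reach 1%. The area grade multiplies the regional severity sum, so a grade of 0 removes the region from the score whatever its redness, thickness and scaliness. A participant whose only remaining disease is a small plaque could then have a PASI of 0 and count as a PASI100 responder with visible disease. Because the assessor enters the grade directly, the SAP formula could not restore a region entered as 0. Complete clearance is a named secondary objective, and with 30 and 15 participants a single reclassification is visible in the reported rate.

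**Working it through.** **Formula and check.** SAP 6.1.5.1: PASI is the sum over regions of weight × (R+T+S) × A, with weights of 0.1 head, 0.2 upper extremities, 0.3 trunk and 0.4 lower extremities. At the maximum, each region has R+T+S = 12 and A = 6, so PASI = (0.1+0.2+0.3+0.4) × 12 × 6 = 72, the upper limit both documents state.

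**What one trace region is worth.** With A = 1 it adds weight × (R+T+S); with A = 0 it adds nothing. For almost-clear lesions I read the IGA 1 descriptor, "No thickening; normal to pink coloration; no to minimal focal scaling", as thickness 0, redness at most 1 and scaling at most 1, so R+T+S runs from 0 to 2. This reading is an assumption. At R+T+S = 2, the lowest eligible Baseline PASI of 12, and no disease in any other region:

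| Trace region | PASI if A = 1 | Improvement | PASI if A = 0 |
|---|---|---|---|
| Head | 0.1 × 2 = 0.2 | 98.3% | 0 |
| Upper extremities | 0.2 × 2 = 0.4 | 96.7% | 0 |
| Trunk | 0.3 × 2 = 0.6 | 95.0% | 0 |
| Lower extremities | 0.4 × 2 = 0.8 | 93.3% | 0 |

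**PASI100.** The cut-off is a score of 0. Where all else is clear, any trace region with R+T+S of at least 1 adds at least 0.1 and decides PASI100 at every Baseline. At R+T+S = 0 the grade makes no difference. A wrong 0 at Week 16 can only add PASI100 responders. One participant is 1/30 = 3.3 points on bimekizumab and 1/15 = 6.7 points on placebo.

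**PASI90.** The cut-off is 10% of Baseline, or 1.2 at Baseline 12. Let P be the score from the other regions. The grade matters only if P is at or below the cut-off and P + weight × (R+T+S) is above it.

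- P = 0: legs at R+T+S = 3 give 1.2, exactly 90%, so the response stands. Legs at 4 give 1.6, or 86.7%, and it is lost.
- P > 0: a trunk properly graded 1 with R+T+S = 2 gives 0.6 (95.0%). Trace legs at R+T+S = 2 add 0 or 0.8, for a total of 0.6 or 1.4 (88.3%). Here one almost-clear region does decide PASI90, and absolute PASI ≤1 as well.

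PASI90 is therefore not immune, but it is touched only near its cut-off. The net direction is not fixed either: a wrong 0 at Week 16 raises the percent improvement, while a wrong 0 at Baseline lowers the starting score and so reduces it.

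**Which grade the documents intend.** The four matching statements reserve grade 0 for *none*. A region with a plaque is not none, so the lowest grade left is 1. SAP 5.3.1.1 then refers to 6.1.5.1, which says the same outright. No reading of the documents assigns 0 to visible disease.

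**Sample size.** The planned 95% power uses 70% versus 13.3% with 30 and 15 participants. The continuity-corrected approximation gives 95.6%. The area wording enters none of these inputs.

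**The case for a change.** The best case for a change is that the SAP cannot repair what the assessor typed. The wording tied to data entry carries the 1% floor, the grade is entered directly, and SAP 5.4.1.3 shows that data collection was under way when the SAP was amended. A literal-minded assessor could enter 0 for a 0.5% plaque, and no later derivation would recover it.

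The premise stands: a wrongly entered 0 is not correctable by formula. Three things limit it.

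- The assessor would have to rate lesions in a region and, on the same form, record that the region has none. That contradicts the label of grade 0.
- The missing-data rule in SAP 6.1.5.1 begins "If the area of affected skin and/or all severity measurements for up to 2 regions are missing", so area and severity are handled as separate items. If both are stored, area 0 beside a non-zero severity score is a contradiction that ordinary data cleaning would catch.
- What the assessor saw is set by the electronic form and the rater instructions. Neither is among the documents, and rewording the protocol or SAP would not alter grades already entered.

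Total BSA is a weaker cross-check. It is captured as "The total BSA affected by PSO will be entered as a percentage from 0 to 100" with no decimals specified, and a trace leg region covers less than 0.4 × 1% = 0.4% of body surface, so it may be recorded as 0.

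**Conclusion.** The inconsistency is a clerical slip: four statements of a scoring band were not brought into line with the fifth. The intended grade for involvement above 0% and below 1% is 1, because grade 0 means no disease and the SAP refers to its own gap-free rule. An analyst who follows the plan as written scores PASI correctly.

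If trace disease had nonetheless been entered as 0, PASI100 would bear most of the effect, at 3.3 points per participant on bimekizumab and 6.7 on placebo. PASI90 and the absolute PASI cut-offs would move only for participants close to those limits. PASI100 is secondary with nominal p-values only. IGA 0, paired with it in the same objective, and IGA 0/1, the other co-primary endpoint, do not use the area grade. Superiority requires both co-primary endpoints.

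This rests on reading *none* in its ordinary sense and on the form and rater instructions not telling assessors to enter 0 for visible disease. The documents give no frequency for trace residual disease, so the number of affected responses cannot be estimated, and no effect on any entry or conclusion has been shown. Aligning the wording would be tidy, but nothing in the analysis depends on it.

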8.1.2 IGA

A static IGA for PSO will be used to assess disease severity in all study participants during the study. The IGA will be completed at the visits specified in the SoA (Table 1-1).

The Investigator will assess the overall severity of PSO using the following 5-point scale presented in Table 8-2 below.

Table 8-2: Five-point IGA

Score	Short descriptor	Detailed descriptor
0	Clear	No signs of PSO; postinflammatory hyperpigmentation may be present
1	Almost clear	No thickening; normal to pink coloration; no to minimal focal scaling
2	Mild	Just detectable to mild thickening; pink to light red coloration; predominately fine scaling
3	Moderate	Clearly distinguishable to moderate thickening; dull to bright red, moderate scaling
4	Severe	Severe thickening with hard edges; bright to deep dark red coloration; severe/coarse scaling covering almost all or all lesions

IGA=Investigator’s Global Assessment; PSO=psoriasis

8.1.3 DLQI

The DLQI is a questionnaire designed for use in adult study participants with PSO. The DLQI is a skin disease-specific questionnaire aimed at the evaluation of how symptoms and treatment affect study participants’ health related QOL. This instrument asks study participants about symptoms and feelings, daily activities, leisure, work and school, personal relationships, and treatment. It has been shown to be valid and reproducible in study participants with PSO. The DLQI score ranges from 0 to 30, with higher scores indicating lower health related QOL. A 4-point change in the DLQI score (DLQI response) has been reported to be meaningful for the study participant (within-subject minimal important difference); while a DLQI absolute score of 0 or 1 indicates no or small impact of the disease on health related QOL (Basra et al, 2015; Hongbo et al, 2005). Study participants will be asked to complete the DLQI as outlined in the SoA (Table 1-1).

8.1.4 Scalp IGA

A static IGA for scalp PSO will be used to assess disease severity on the scalp.

The scalp IGA will be assessed for all study participants at Baseline. The scalp IGA will be completed by the Investigator electronically. Only study participants with a scalp IGA score >0 at Baseline will have the scalp IGA assessed at later visits as specified in the SoA (Table 1-1).

Scalp lesions will be assessed in terms of clinical signs of redness, thickness, and scaliness using a 5-point scale (Table 8-3).

Table 8-3: Scalp IGA

Score	Short descriptor	Detailed descriptor
0	Clear	Scalp has no signs of PSO; postinflammatory hyperpigmentation may be present
1	Almost Clear	Scalp has no thickening; normal to pink coloration; no to minimal focal scaling
2	Mild	Scalp has just detectable to mild thickening; pink to light red coloration; predominately fine scaling

Table 8-3: Scalp IGA

Score	Short descriptor	Detailed descriptor
3	Moderate	Scalp has clearly distinguishable to moderate thickening; dull to bright red, moderate scaling
4	Severe	Scalp has severe thickening with hard edges; bright to deep dark red coloration; severe/coarse scaling covering almost all or all lesions

PSO=psoriasis

8.1.5 PSD (P-SIM) responses

UCB developed a new electronic patient-reported outcome (ePRO) measure that will be used to assess key symptoms relevant to study participants with moderate to severe plaque PSO. PS0010 used the draft ePRO measure in selected countries to enable psychometric validation of the ePRO.

The PSD (P-SIM) consists of 14 items, measuring the following PSO-related signs, symptoms, and functional impacts: redness, scaling, cracking, lesions, thickening, itch, pain, burning, dryness, irritation, sensitivity, fatigue, embarrassment, and choice of clothing. Each item is assessed for severity/impact level over a recall period of the past 24 hours on a 0 to 10 scale, where 0 means no symptoms or impact and 10 means very severe symptoms or worst impact.

Site staff will train study participants on the use of the ePRO diary at the Screening Visit, following which the device will be dispensed to the study participant for home use until the Week 16 Visit. The ePRO diary will be completed on a daily basis from Screening to the Week 16 Visit.

The ePRO diary software will be programmed such that the study participants will be given a window of opportunity to complete the ePRO diary. The data collected on the ePRO diary will be uploaded to a central server database and will be 21 CFR Part 11 compliant. Appropriate Good Clinical Practice (GCP) procedures (including study participant/site training and testing) will be performed at the study sites.

8.2 Safety assessments

Planned timepoints for all safety assessments are provided in the SoA (Table 1-1).

8.2.1 Physical examination

A physical examination will be performed at the visits specified in the SoA (Table 1-1). The physical examination will include general appearance; ear, nose, and throat; eyes, hair, and skin; respiratory; CV; GI; musculoskeletal; hepatic; neurological (including limb reflexes); and mental status. All physical examinations will also include evaluation of signs and symptoms of active TB and risk for exposure to TB (Section 8.2.7.3). Findings considered clinically significant changes since the physical examination at the Screening Visit will be recorded as AEs.

Investigators should pay special attention to clinical signs related to previous serious illnesses.

8.2.2 Vital signs

Vital signs will be collected at every visit and will include systolic and diastolic blood pressure (BP), pulse rate, and body temperature (oral, axillary, or otic). Study participants should be sitting for 5 minutes before and during vital signs assessments.

Vital signs should be assessed prior to IMP administration and prior to any blood collection.

8.2.3 12-lead ECGs

Twelve-lead standard ECGs will be recorded at the Screening and Week 16 visits and read by a central ECG reader. Full details of ECG recording will be provided in the ECG Manual.

8.2.4 PHQ-9

The PHQ-9 is a multipurpose instrument for screening, diagnosing, monitoring, and measuring the severity of depression (Kroenke et al, 2001). The PHQ-9 scores for depression range from 0 to 27 with higher scores indicating a worse state. A score of 5 to 9 is considered to be minimal symptoms of depression. A score of 10 to 14 is considered minor depression, dysthymia, or mild major depression. A score of 15 to 19 is considered to indicate moderately severe major depression, and a score ≥ 20 is considered to be severe major depression.

Refer to Section 7.1 for PHQ-9-related IMP discontinuation criteria.

8.2.5 Clinical safety laboratory assessments

All protocol-required laboratory assessments, as defined in Section 10.2, must be conducted in accordance with the laboratory manual and the SoA (Table 1-1). See Section 10.2 and the SoA for the list, timing, and frequency of clinical laboratory tests to be performed.

The Investigator must review the laboratory report, document this review, and record any clinically significant changes occurring during the study in the AE section of the eCRF. The laboratory reports must be filed with the source documents. Clinically significant abnormal laboratory findings are those which are not associated with the underlying disease, unless judged by the Investigator to be more severe than expected for the study participant's condition.

All laboratory tests with values considered clinically significantly abnormal during participation in the study or within 20 weeks after the last dose of IMP should be repeated until the values return to normal or Baseline or are no longer considered clinically significant by the Investigator or Medical Monitor. If such values do not return to normal/Baseline within a period of time judged reasonable by the Investigator, the etiology should be identified and the Sponsor notified.

If laboratory values from nonprotocol specified laboratory assessments performed at the institution's local laboratory require a change in study participant management or are considered clinically significant by the Investigator (eg, SAE or AE or dose modification), then the results must be recorded in the eCRF.

